Mitochondrial/ER ceramides decrease after insulin sensitizing lifestyle intervention - Pilot data for a combined weight loss/exercise training intervention show decreased whole cell ceramide content, as shown before (11; 15) (Figure 8). However, the decrease in whole cell ceramide content comes only from a decrease in mitochondrial/ER ceramide. These data point to an important role of mitochondrial/ER ceramides on insulin sensitivity in vivo.

Mitochondrial/ER DAG accumulates in lean insulin sensitive individuals. Preliminary data show mitochondrial/ER 1,2- and 1,3-DAG were

Figure 2. Sarcolemmal di-saturated DAG content by group (A), and by insulin sensitivity (B) in lean, obese, and type 2 diabetics. Values are means +/- SEMC # significantly different than lean, p<0.05.

Figure 3. PKCE activation in lean, obese, and type 2 diabetics. Values are means +/- SEM. #= significantly different than lean, p<0.05.

Figure 4. Sarcolemmal C18:0 ceramide content by group (A), and by insulin sensitivity (B) in lean, obese, and type 2 diabetics. Values are means +/- SEM. #= significantly

different than lean, p < 0.05.

higher in lean individuals compared to obese or type 2 diabetic volunteers (Figure 9), with the greater DAG content distributed over most species. These data are counterintuitive, but may reflect the greater content of mitochondria in lean individuals compared to obese volunteers with and without diabetes, and/or increased mitochondrial fission/fusion (29; 30).

Mitochondrial/ER DAG increase after weight loss and exercise training.

Preliminary data from a weight loss and exercise training intervention show an increase in mitochondrial/ER 1,2-DAG after the intervention (Figure 10). These data are consistent with some reports in the literature where DAG concentration was increased in endurance trained athletes (13). These data agree with Figure 9 and suggest mitochondrial/ER DAG accumulation may be a previously unrecognized adaptation to exercise training and/or weight loss.

Insulin resistant muscle accumulates long chain acyl-carnitines and shows oxidative

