Every attempt will be made to minimize the risks involved to patients in this study. Subjects privacy, autonomy and confidentiality will be protected with redundant IRB & HIPAA-compliant measures. Subjects may withdraw from the study at any time. Only state-of-the-art techniques will be used in a NIH-funded, JCAHO accredited CTRC facility. CTRC personnel are exquisitely trained, and emergency equipment is easily accessible on-site. Universal precautions will be taken to protect everyone involved with subject testing. Sterile technique is invoked where appropriate. All infusion are prepared and stored by a licensed pharmacist and tested for sterility and pyrogenicity. We will also have an independent safety officer who will evaluate subject risk annually. Taken together, these measures have proven successful in the minimization of risk to subjects. Protected and de-identified information will be kept on password-protected computer systems with hard copies in locked filing cabinets in locked offices.

E. Potential Scientific Problems:

We have extensive experience recruiting individuals across the metabolic spectrum (51-55), as well as performing insulin clamps (39; 51; 56; 57), and muscle biopsies (26; 43; 51; 53; 58-61) and therefore no problems are expected with the proposed studies. An alternative approach to our proposal would be to use a combined exercise and weight loss intervention, which may have more dramatic results compared

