Aim 2: Our statistical methods are rigorous with an *a priori* statistical analysis plan to test our hypothesis in an unbiased manner, and power analysis based on our own preliminary data. Data will be analyzed for normality, and any non-normally distributed variables will be log-transformed for use in analytic models. Correlations between the change in mitochondrial/ER DAG and sphingolipid species and the change in insulin sensitivity, mitochondrial respiration, ROS production, acyl-carnitine species, and ER stress will be performed using Pearson's correlations coefficient in the overall study group. Data comparing changes in mitochondrial/ER DAG and sphingolipid species to changes in insulin sensitivity and parameters of mitochondrial respiration between groups before and after the intervention will be analyzed using a oneway ANOVA (SAS statistical software ver. 9.4, Cary, NC). If overall differences are observed by group then individual group comparisons will be made using Tukey's procedure, which corrects for family-wise error rates. Changes in individual DAG and ceramide species will be examined using the Benjamini Hochberg procedure to limit false discoveries, and changes in groups of DAG and ceramide species will be examined using PCA as described in Aim #1. Our power analysis is based on our preliminary data for the change in mitochondrial ceramide and DAG species after the pilot intervention shown in Figures 8 and 10, and assuming there will be no significant changes in the control intervention. With an overall n of 51, we will have 99% power to detect a Pearson correlation coefficient as large as that observed in our preliminary data (Figure 7B, r= -0.44), and we will have 80% power to detect a correlation coefficient as small as -0.38. With an n of 17/group, we will have 95% power to measure a similar change in mitochondrial DAG and sphingolipids as we have observed in our pilot data after the weight loss or exercise interventions using pairwise comparisons in ANOVA models using the Tukey procedure. The type 1 error rate (alpha) will be set at 5% for all comparisons.

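### Aim 2's 95% pairwise power rests on a combined weight-loss-and-exercise pilot, so it is not established for the single-intervention arms that the trial randomises

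*Combined protocol and SAP*

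**What the plan says.** In section IV.F (Data Analysis Plan, Aim 2), the power analysis is based on the "change in mitochondrial ceramide and DAG species after the pilot intervention shown in Figures 8 and 10", with no change assumed in the control group. The plan then claims 95% power, at 17 per group, for a "similar change in mitochondrial DAG and sphingolipids as we have observed in our pilot data after the weight loss or exercise interventions", tested pairwise with Tukey's procedure at a 5% type 1 error rate.

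Section III (Preliminary Studies/Progress Report) describes the two figures. For Figure 8: "Pilot data for a combined weight loss/exercise training intervention show decreased whole cell ceramide content"; that fall is said to come only from the mitochondrial/ER fraction. For Figure 10: "Preliminary data from a weight loss and exercise training intervention show an increase in mitochondrial/ER 1,2-DAG after the intervention".

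Section IV.C randomises to endurance exercise without weight loss, diet-induced weight loss, or delayed-intervention control. No arm receives both components. Section IV.E mentions, as an alternative design, to "use a combined exercise and weight loss intervention, which may have more dramatic results compared" with either component alone. The Aim 1 power statement, also in IV.F, attributes its own pilot change to the combined intervention.

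**The concern.** The Aim 2 sentence presents the effect behind the 95% as one seen after weight loss or after exercise, which are the trial's two active arms. The figures it relies on show the effect of both together. A reader of IV.F alone would think the assumed effect had already been observed in arms like those being randomised.

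Mitochondrial/ER total DAG and ceramide are primary outcomes for Aim 2 (section IV.A), so the statement bears on how main results are read. If 95% power is taken to apply to each active arm, a non-significant change in that arm looks like strong evidence of no effect. If one intervention gives clearly less than the combined change, a non-significant result says much less.

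**Working it through.** **1. Source of the effect.**

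| Place | How the intervention is described |
|---|---|
| III, Figure 8 | weight loss and exercise combined |
| III, Figure 10 | weight loss and exercise together |
| IV.F, Aim 1 pilot | combined |
| IV.F, Aim 2, basis of the power analysis | one pilot intervention, singular, Figures 8 and 10 |
| IV.F, Aim 2, the 95% sentence | weight loss or exercise, plural interventions |
| IV.C, randomised arms | exercise alone, diet alone, control |

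The 95% sentence is the one entry that describes the pilot as separate interventions. Section IV.C does cite pilot results under each programme: a 9% rise in VO₂max for exercise, and 9% weight loss with a 62% rise in insulin sensitivity for the diet. It gives no lipid change there, so it supplies no single-intervention effect for this calculation.

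**2. Can the 95% be reproduced?** No. The Aim 2 pilot mean change and SD are not in the text and the figures are not shown. The calculation can only be inverted, to find the standardised difference that gives 95%.

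Inputs: 17 per group, 3 groups, 5% alpha, Tukey (all from the plan).
- Error degrees of freedom: 3 × (17 − 1) = 48.
- Critical t: q(0.95; 3, 48)/√2 = 3.420/1.414 = 2.418.
- Noncentrality for a difference of d SD: d × √(17/2) = 2.915d.
- Power = P(noncentral t on 48 df > 2.418); the opposite tail is negligible.

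Results:
- 95% power: d = 1.406 (noncentrality 4.10).
- 80% power: d = 1.122.

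These two values describe the design and hold whatever the pilot showed. Other test choices put the 95% point at 1.24 SD (normal approximation), 1.26 (unadjusted ANOVA t), 1.28 (two-sample t) and 1.43 (Bonferroni).

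**3. Illustration: one intervention gives a fraction f of the combined change.** Assumptions, none of them from the documents: the stated 95% is correct (so the combined change is 1.406 SD), the SD is the same, and control does not change.

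| f | d = f × 1.406 | Tukey power against control |
|---|---|---|
| 1 | 1.41 | 95% |
| 0.9 | 1.27 | 89% |
| 0.8 | 1.12 | 80% |
| 2/3 | 0.94 | 62% |
| 1/2 | 0.70 | 36% |

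A simulation of 100,000 trials that required a significant overall ANOVA first gave 95%, 74% and 36% at f = 1, 0.75 and 0.5, in line with the formula (0.742 at f = 0.75).

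**4. How much depends on the inverted effect.** Aim 1 prints a change of 0.041 with SD 0.02, so d = 0.041/0.02 = 2.05 if 0.02 is the SD of the change. Its stated 84.6% inverts to d = 1.185. Inverting a stated power in this plan therefore need not recover the pilot effect. If the Aim 2 combined effect were also 2.05 SD (an assumption), power would be 94% at two thirds (d = 1.37) and 71% at half (d = 1.03).

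**The case against.** The strongest reply is that the 95% is conditional: it is the power for a similar change, and nothing shows it was miscalculated. That stands, and the point is one of attribution. A reader might infer an arithmetic error, but with no Aim 2 mean or SD in the text the documents cannot support that.

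The sentence can also be parsed so that the reference to weight loss or exercise describes changes to be measured in the trial, not the pilot. The plural noun and the following reference to pairwise comparisons give this some support, and the figures are cited and described elsewhere. But on that reading the plan still applies a combined effect to single-intervention arms without saying so. Aim 1 applies a combined pilot to the same arms; the difference is that Aim 1 labels it.

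Three stronger inferences are tempting and not supported:
- **That the single arms have 62% or 36% power.** Those figures need the inverted effect and an assumed fraction. Section III leaves open that the DAG rise came from exercise, weight loss or both, so one component could carry it all.
- **That the protocol expects larger combined effects.** Section IV.E says only that they may be more dramatic; its fallback to a combined intervention concerns insulin sensitivity, not lipids.
- **That no single-intervention pilot data exist.** The documents report no such lipid data; the investigators may hold some.

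It is also fair that the plan nowhere says a non-significant arm will be read as no effect, and that Aim 2 relies partly on correlations across the whole group. This limits the consequence but does not correct the sentence.

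**Conclusion.** The point holds as a misattributed effect behind a stated power. The 95% is the power if a single-intervention arm matches the combined pilot change, and the documents do not establish that for either active arm. This conclusion needs only the plan's own descriptions of Figures 8 and 10 and of the randomised arms.

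The size of any shortfall is unknown. With 17 per group and Tukey on 48 df, a single arm must differ from control by about 1.12 SD for 80% power and 1.41 SD for 95%. If the 95% is taken as correct, with equal SDs and no control change, an arm keeps 80% power only if it achieves about 80% of the combined change (1.122/1.406 = 0.80). A larger true pilot effect would make the loss smaller.

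**What to change.** Reword the Aim 2 power sentence in section IV.F:
- Say that the pilot change was observed after the combined weight loss and exercise intervention, and print the mean change and SD used.
- State what the design can detect regardless of the pilot: with 17 per group and Tukey's procedure, 80% power for a difference of about 1.12 SD and 95% for about 1.41 SD. Do not present 1.41 SD as the pilot effect.
- Add that power is lower if one intervention gives less than the combined change. Any figures (about 89%, 80%, 62% and 36% at 90%, 80%, two thirds and half) should be marked as illustrations that assume the 95% is correct and the SD unchanged; once the pilot mean and SD are printed, recompute them from those.
- Say that non-significant single-arm results will be interpreted from confidence intervals for the difference from control.

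No change to the sample size is needed. The cost is a short rewording and a less favourable power statement.
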